6.13.2. Adverse Events

Unless otherwise specified, AEs will be reported using the MedDRA system organ class (SOC) and preferred term (PT). Selected AEs may be reported using MedDRA high-level terms (HLT), in addition to the SOC and PT, for consistency with other dulaglutide studies. Treatment-

emergent AEs are defined as events that are newly reported after the first dosing or reported to worsen in severity from the first dosing.

Summary statistics will be provided for the following data: medical history and/or pre-existing condition AEs, TEAEs, SAEs, TEAESIs, and study discontinuations due to death or AEs. For TEAEs, SAE and TEAESIs will be reported separately from baseline to the end of the treatment period, and to the end of the study including safety follow-up. The number and proportions of patients experiencing each corresponding AEs will be reported for each randomized treatment group. Chi-square or Fisher's exact tests will be used to compare the randomized treatment groups detailed in Section 6.1.

The incidence of patients with at least one TEAE will be reported, and the proportion of patients experiencing each reported TEAE will be presented by PT (descending order) and by randomized treatment group, and also by the SOC (alphabetical order) and by descending PT order within the SOC. The proportion of patients experiencing each reported TEAE that are assessed as related to the study disease, study drug device, or procedures will be summarized. Note, drug device is coded as concomitant device. Additionally, a summary of TEAEs by maximum severity will be presented descriptively by randomized treatment group.

Separate summary reports will be provided for the number and percentage of patients who discontinued from the study and for patients who discontinue study treatment due to AE or death by descending frequency PT and within SOC by the randomized treatments. If deemed necessary, a Bayesian model may be fitted to evaluate if the probability of the incidence of discontinuation due to AEs for any investigational dose being $\leq 10\%$, $\leq 15\%$.

Listings will be provided for SAEs, TEAEs, and discontinuations due to AE or death.

Additional analyses will be performed for the purpose of fulfilling the clinical trial registry (CTR) requirements (Section 6.19).

6.13.3. Deaths, Other Serious Adverse Events, and Other Notable Adverse Events

All SAEs will be summarized by treatment by PT term using descending frequency order, and by SOC and PT (descending frequency order within SOC). Death will be listed including both adjudicated and investigator reported. Patient listings for the patient narratives will be generated for further processing. The criteria for patient narratives will be provided by the trial medical team and will be documented in eTMF.

6.13.4. Adverse Events of Special Interest

6.13.4.1. Hypoglycemic Episodes

Summary reports will include both incidence and rates of hypoglycemia in the ITT population by censoring the post rescue data. Hypoglycemia will be analyzed as documented symptomatic, asymptomatic, probable, severe, total, and nocturnal hypoglycemia with the definition (American Diabetes Association 2005) below:

- **Documented symptomatic hypoglycemia:** any time a patient feels that he/she is experiencing symptoms and/or signs associated with hypoglycemia, and has a PG level of ≤ 70 mg/dL (≤ 3.9 mmol/L).
- **Asymptomatic hypoglycemia:** any event not accompanied by typical symptoms of hypoglycemia, but with a measured PG ≤ 70 mg/dL (≤ 3.9 mmol/L).
- **Probable symptomatic hypoglycemia:** an event during which symptoms of hypoglycemia are not accompanied by a PG determination (but that was presumably caused by a PG concentration ≤ 70 mg/dL [≤ 3.9 mmol/L]).
- **Severe hypoglycemia:** an episode requiring the assistance of another person to actively administer carbohydrate, glucagon, or other resuscitative actions. These episodes may be associated with sufficient neuroglycopenia to induce seizure or coma. Plasma glucose measurements may not be available during such an event, but neurological recovery attributable to the restoration of PG to normal is considered sufficient evidence that the event was induced by a low PG concentration.
- **Total hypoglycemia:** any event of documented symptomatic, asymptomatic, probable, unspecified, severe hypoglycemia. Unspecified hypoglycemia is defined as an event during which PG ≤ 70 mg/dl (3.9 mmol/l) but no information relative to symptoms of hypoglycemia was recorded.
- **Nocturnal hypoglycemia:** any total hypoglycemic event that occurs between bedtime and waking.

A different glucose threshold of <54 mg/dL (<3 mmol/l) may also be included in these analyses when deemed appropriate.

For each category of the aforementioned hypoglycemia categories, the incidence will be analyzed using the methods for analyses of categorical data described in Section 6.1, by visit and by randomized treatment; the rate of hypoglycemic episodes will be analyzed using a generalized linear mixed-effects model assuming negative binomial distribution for hypoglycemic episodes with pooled country, treatment, visit, and treatment-by-visit interaction as fixed effects and baseline HbA1c and baseline rate as covariates. The logarithm of days between visits will be adjusted as an offset to account for possible unequal duration between visits and between patients. This model will be implemented using SAS® procedure GLIMMIX using the log link function. The predicted hypoglycemia rate per 1-year by treatment and by visit will also be presented. An unstructured covariance structure will be used to model the within-patient errors. If this analysis fails to converge, the following covariance structures will be tested in this order: compound symmetry, then autoregressive. For rare hypoglycemic episodes such as severe hypoglycemia, stratified Wilcoxon rank sum test will be used to test 1-year corresponding hypoglycemia rate between each dulaglutide dose and placebo, and between each 2 higher dose and dulaglutide 1.5 mg.

A listing of individual hypoglycemic episodes by patient will be presented.

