###### **7.4.1.2. Management of Increased Hypoglycemia Risk**

Dulaglutide and metformin are non-secretagogues; therefore, clinically relevant increases in the risk of hypoglycemia are not expected in this trial (Trulicity USPI [WWW]).

In this study, increased risk of hypoglycemia is defined as having a single episode of severe hypoglycemia or having more than 1 episode of documented symptomatic hypoglycemia within a 1-week period at any time during the treatment period.

In cases where a patient experiences hypoglycemia as described above, to confirm the increased risk, the study sites must ensure that the patient has been fully compliant with the assigned therapeutic regimen and also that there is no evidence of other possible causes of hypoglycemia (for example, omission of meal, unexpected increase in exercise).

Patients fulfilling the definition of increased risk of hypoglycemia should first decrease the metformin dose, followed by discontinuation of metformin, if needed. If the patient continues to experience hypoglycemic events after the discontinuation of metformin, the investigator should discontinue the patient from study drug. No adjustment of the dulaglutide dose should be made.

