#### **10.3.4.3. Hypoglycemic Episodes**

Section [9.2.2.1](#) contains definitions of categories of hypoglycemia. A listing of individual hypoglycemic episodes by patient will be presented. Summary reports will include both incidence and rates of hypoglycemia. Hypoglycemia will be analyzed as documented symptomatic, asymptomatic, probable, severe, or nocturnal and for all events combined as total hypoglycemia. Other categories, including the categories above defined with different glucose thresholds, may also be included in these analyses when deemed appropriate.

The incidence will be analyzed using the categorical methods described in Section [10.3.1](#) and rate of hypoglycemic episodes will be analyzed using a generalized linear mixed-effects model assuming negative binomial distribution for hypoglycemic episodes. Incidence and rates will be summarized for each treatment arm and entire treatment period.

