5.2. Determination of Sample Size

Assuming a screen failure rate of 30%, approximately 429 patients will need to be screened to attain approximately 300 patients randomized to the 4 treatment arms in a 1:1:1:1 ratio for 4.5 mg, 3.0 mg, 1.5 mg dulaglutide, or placebo weekly (~75 patients per arm). For the investigational dulaglutide dose arms (4.5 mg and 3.0 mg), approximately 38 patients will be assigned to each titration algorithm (Algorithms 1 and 2). Assuming a 20% dropout, this will result in approximately 60 patients per arm and 30 patients per algorithm (in each of the investigational-dose dulaglutide arms) completing the study.

The aforementioned sample size provides $\geq 90\%$ power to demonstrate superiority for the dulaglutide doses (4.5 mg, 3.0 mg, and 1.5 mg) to placebo with respect to HbA1c change from baseline to 18 weeks. This assumes a true glycemic effect difference of -1% HbA1c for each dulaglutide dose versus placebo, and a standard deviation (SD) of 1.2% with a 2-sided alpha of 0.05.

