6.1. General Considerations

Statistical analysis of this study will be the responsibility of Eli Lilly and Company or its designee. Any change to the data analysis methods described in the protocol will require an amendment ONLY if it changes a principal feature of the protocol. Any other change to the data analysis methods described in the protocol, and the justification for making the change, will be described in the statistical analysis plan (SAP) or the clinical study report (CSR). Additional exploratory analyses of the data may be conducted as deemed appropriate without further changes made to the protocol or SAP even after the datalock.

Countries with fewer than 10 randomized patients will be pooled for statistical analyses. Pooled country will be employed for all formal statistical model-based analyses as a block factor unless otherwise denoted.

Unless otherwise specified, all tests of treatment effects will be conducted at a 2-sided alpha level of 0.05, and confidence intervals (CIs) will be calculated at 95%, 2-sided. All tests of interactions between treatments and factors of interest will be conducted at a 2-sided alpha level of 0.10. No adjustments for multiplicity will be performed.

The baseline visit will be Visit 3. For all variables, including HbA1c, if baseline data are not available or are missing, the last nonmissing measurement taken prior to this visit will be used for the baseline measurement. The efficacy measure for the primary analysis is defined as the change from baseline in HbA1c to Week 18 (Visit 12).

For all statistical analyses, missing data will be treated as missing at random unless otherwise specified; therefore, no imputation is needed unless otherwise stated.

The treatment groups mentioned in this document are based on the randomized treatment groups: dulaglutide 4.5 mg, dulaglutide 3.0 mg, dulaglutide 1.5 mg, placebo. For the purposes of tables, figures, the treatment groups will be: Dula 4.5, Dula 3.0, Dula 1.5, and Placebo. For data listings, the treatment groups will be presented as Placebo, Dula 1.5, Dula 3.0/A1 representing dulaglutide 3.0 mg/algorithm 1, Dula 3.0/A2 representing dulaglutide 3.0 mg/algorithm 2, Dula 4.5/A1 representing dulaglutide 4.5 mg/algorithm 1, Dula 4.5/A2 representing dulaglutide 4.5 mg/algorithm 2.

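### For sparse hypoglycemia categories the treatment-by-visit rate model will have empty cells, so its by-visit and visit-averaged rates break down; a whole-period, one-record-per-patient model should be primary

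*SAP*

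**What the plan says.** SAP 6.13.4.1 applies one rate model to each hypoglycemia category: a generalized linear mixed model in GLIMMIX, negative binomial with log link, "with pooled country, treatment, visit, and treatment-by-visit interaction as fixed effects and baseline HbA1c and baseline rate as covariates". It adds: "The logarithm of days between visits will be adjusted as an offset". The within-patient covariance is unstructured. If the fit fails to converge, compound symmetry and then autoregressive are tried. For rare episodes, with severe hypoglycemia as the example, a stratified Wilcoxon rank sum test on the annualized rate is used; no cut-off defines rare. The model-based output named is a predicted annual rate by treatment and by visit. Post-rescue data are censored.

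Protocol 10.3.4.3 also names a negative binomial generalized linear mixed-effects model, but describes the reporting differently: "Incidence and rates will be summarized for each treatment arm and entire treatment period".

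On frequency, Protocol 7.4.1.2 says that "clinically relevant increases in the risk of hypoglycemia are not expected in this trial", and Protocol 3.2 describes the risk with dulaglutide as low. Neither document gives a number.

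**The concern.** A model with a separate parameter for every arm at every visit needs events in every cell. Under a log link, the maximum-likelihood log rate of a cell with no events is minus infinity. Software stops at some large negative number, and may report that it has converged. The cell's predicted rate is then effectively zero with a meaningless standard error, and any arm summary that averages the cell estimates on the log scale is pulled down with it.

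Neither fallback in the SAP removes this. The covariance sequence leaves the fixed effects as they are, and it is triggered only by reported non-convergence. The Wilcoxon test avoids empty cells but gives no model-based rate, and without a threshold for rare the plan does not say which categories go to which method.

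The rate of severe, total, documented symptomatic and nocturnal hypoglycemia is a secondary safety endpoint. The risk is a tabulated rate that is badly wrong, or a choice of method made once the counts are known.

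**Working it through.** **Sample size behind the cell counts.** SAP 5.2 plans to "attain approximately 300 patients randomized to the 4 treatment arms in a 1:1:1:1 ratio", which is 75 per arm, and continues: "Assuming a 20% dropout, this will result in approximately 60 patients per arm". Check: 75 × 0.80 = 60; 300 / 0.70 = 428.6, which rounds to the stated 429 screened. The stated HbA1c power of at least 90% also reproduces: with 60 per arm, difference 1.0 and SD 1.2 it is 99.5%. No figure is stated for hypoglycemia.

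**Cells.** The Schedule of Activities records hypoglycemic events at Visits 4 to 12 (Weeks 2, 4, 6, 7, 8, 9, 10, 14, 18). The nine intervals last 2, 2, 2, 1, 1, 1, 1, 4 and 4 weeks. SAP Appendix 1 excludes hypoglycemia from its analysis windows, so the one-week intervals are not merged.

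- Treatment-by-visit cells: 4 × 9 = 36, of which 16 are one-week, 12 two-week and 8 four-week.
- Unstructured covariance: 9 × 10 / 2 = 45 parameters.
- Patient-years per cell at 75 per arm: 75/52 = 1.44, 150/52 = 2.88 and 300/52 = 5.77.

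**Chance that a cell is empty.** Let m = rate × weeks/52 be the expected events per patient in the interval, n the patients per arm and k the dispersion.

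- Poisson: P0 = exp(−n·m).
- Negative binomial: P0 = (1 + k·m)^(−n/k).
- Expected empty cells = 16·P0(1 wk) + 12·P0(2 wk) + 8·P0(4 wk).

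Example at 1 event per patient-year, Poisson, n = 75: P0 = exp(−1.44) = 0.236, exp(−2.88) = 0.056 and exp(−5.77) = 0.003. Expected empty cells = 16(0.236) + 12(0.056) + 8(0.003) = about 4.5.

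The rates below are assumptions. Each range runs from Poisson to k = 4, with n = 75, full follow-up and cells treated as independent for the last two columns:

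| Events per patient-year | Expected empty cells of 36 | A given arm has at least one | Any arm has at least one |
|---|---|---|---|
| 0.25 | 19 | >99% | about 100% |
| 0.5 | 11 | 97–98% | about 100% |
| 1 | 4.5–4.9 | 72–75% | >99% |
| 2 | 0.9–1.2 | 21–26% | 62–70% |
| 3 | 0.2–0.3 | 5–8% | 19–29% |
| 5 | <0.1 | <1% | 1–4% |

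With 60 per arm, the expected number at 1 per patient-year rises to 6.3–6.8.

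**Effect on the estimates.** One simulated data set at each of three rates was fitted with a log-link negative binomial marginal model on the 36 cells, using independence, compound symmetry and autoregressive structures.

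- 0.3 per patient-year: 24 empty cells. The lowest log rates were −27 to −31, and arm rates averaged over visits on the log scale were essentially 0 under all three structures. Observed arm rates were 0.08 to 0.39.
- 1 per patient-year: 4 empty cells. The three arms containing them had log-averaged rates of 0.001 to 0.10, against observed rates of 1.04 to 1.43.
- 3 per patient-year: no empty cells, and all rates finite.

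In every data set the time-weighted sum of fitted cell rates equalled crude events per exposure. These fits were in Python with fixed working dispersion and no covariates; GLIMMIX and the unstructured fit were not run.

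**Whole-period alternative.** One record per patient gives 75 × 18/52 = 26.0 patient-years per arm. The chance that at least one of four arms has no events, for k from 0 to 10, is 72–76% at 0.05 per patient-year, 27–37% at 0.1, 2–8% at 0.2, 0.2–2% at 0.3 and at most 0.2% at 0.5 or more.

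**The case against.** The strongest reply is that the event rate is unknown. Protocol 7.4.1.2 speaks of increases in risk, not of frequency. Total hypoglycemia under the SAP includes asymptomatic and unspecified glucose values at or below 70 mg/dL, and patients measure fasting glucose daily and a four-point profile weekly. That category could reach 3 or more per patient-year, where empty cells are few. This stands: the point is conditional and applies category by category.

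A reader might infer that arm-level rates become inestimable. The documents do not support that. Protocol 10.3.4.3 asks for rates to be summarized per arm over the treatment period, which crude events per exposure does whatever the model returns. Nor does the SAP name a visit-averaged arm rate as an output; that failure arises only if one is formed on the log scale, as default least-squares means would be.

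A reader might also infer that the SAP has no answer for rare events. It has: the Wilcoxon test is prespecified, severe is given as an example rather than a limit, and it supplies the comparisons with placebo and with 1.5 mg. What is missing is the threshold and a model-based rate.

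On the offset, the SAP does not say whether the interval containing rescue ends at rescue. It would be wrong to assert that days not at risk are counted; the text is silent, and at most one interval per rescued patient is affected.

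Finally, the stakes are limited. The study is exploratory, incidence is tested separately, and the interim criteria in SAP 6.16.2.2 do not rest on this model.

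**Conclusion.** The concern holds for sparse categories. At or below about 1 event per patient-year with 75 patients per arm, at least one empty cell is nearly certain. The by-visit predicted rates for those cells, and any arm rate or contrast averaged over visits on the log scale, would then diverge or be biased strongly toward zero, possibly with convergence reported. Changing the covariance structure does not alter this. At about 2 per patient-year the problem is likely but confined to about one cell; at 3 or more it mostly disappears.

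This rests on assumed event rates, because the documents give none. A claim that the model will fail for every category would go too far. Crude rates per arm, the incidence analyses and the rank test for rare categories remain usable. The change is worth making because it is cheap and matches the reporting period that the protocol names.

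**What to change.** In SAP 6.13.4.1:

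- Make the primary rate analysis one record per patient: negative binomial regression of total episodes in the treatment period on treatment and baseline HbA1c, adding baseline rate and pooled country where estimable.
- Set the offset to the log of days at risk, from first dose to the earlier of rescue or end of treatment. This also settles the silence about the rescue interval.
- Present by-visit rates descriptively.
- Keep the stratified Wilcoxon test, with crude rates, for categories below a stated event count, for example any arm with no events. The whole-period model also fails there, and at 0.1 per patient-year or less that outcome is common.
- Carry the same form into SAP 6.13.5 if a similar model is used for gastrointestinal events.

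The cost is SAP wording and simpler code. Model-based by-visit rates are lost, and the analysis is no longer the mixed-effects model named in Protocol 10.3.4.3, so the departure and its reason should be recorded in the SAP, as SAP 6.1 allows for changes that do not alter a principal feature of the protocol.

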6.13.4.2. Severe, Persistent Hyperglycemia

Summaries (if appropriate) will be provided for events of severe, persistent hyperglycemia (Protocol Section 7.4.1.3) resulting in initiation of rescue therapy by each randomized treatment. The time to the first rescue therapy use will be analyzed using PROC LIFETEST to generate Kaplan-Meier (KM) curves for each treatment. The summary reports will be only generated if more than 3% patients receive rescue intervention.

The patients who experienced severe, persistent hyperglycemia will be listed.

6.13.4.3. Pancreatitis

Summaries of adjudicated and investigator-reported pancreatic events will be provided by each randomized treatment. However, the summary report will only be generated if more than 3% patients have pancreatic event(s). Determination of investigator-reported events will be through the “Acute pancreatitis” Standardized MedDRA Queries (SMQ) and a “Chronic pancreatitis” Lilly Search Categories (LSC) of the AE database, while adjudication-confirmed pancreatitis will be found from adjudication CRF.

The patients developing pancreatitis will be listed separately for the investigator-reported and the adjudicated events.

Each pancreatic enzyme at Week 6 and Week 18, and the maximum post-dose value will be summarized by each randomized treatment, dulaglutide 3.0 mg/algorithm 1, dulaglutide 3.0 mg/algorithm 2, dulaglutide 4.5 mg/algorithm 1, dulaglutide 4.5 mg/algorithm 2, algorithm 1, and algorithm 2 in a shift table using >1 upper limit normal (ULN), and ≥ 3 ULN separately for the ITT population, ITT population with normal baseline, ITT population with baseline value $>$ ULN.

A MMRM with pooled country, baseline HbA1c strata, treatment, visit, and treatment-by-visit interaction as fixed effects will be fitted to analyze each pancreatic enzyme (p-amylase and lipase). In this model, the log transformed ratio (post first dose measure/baseline measure) will be the response variable and log transformed baseline measure instead of baseline measure will be a covariate. The variance-covariance structure selection is detailed in Section 6.1. The treatment in the model will include placebo, dulaglutide 1.5 mg, dulaglutide 3.0 mg/algorithm 1, dulaglutide 3.0 mg/algorithm 2, dulaglutide 4.5 mg/algorithm 1, dulaglutide 4.5 mg/algorithm 2. The report from this analysis will include:

- 1) Geometric LS means and corresponding 95% CIs for each randomized treatment at each scheduled visit, and the ratio in geometric LS means, corresponding 95% CI along with p-value compared relative to placebo and to dulaglutide 1.5 mg at the same visit.
- 2) Geometric LS means and corresponding 95% CIs of pancreatic enzyme for algorithm 1, algorithm 2 after adjusting for baseline, and the ratio between algorithm 2 and algorithm 1 (using algorithm 1 as reference) at Week 6 (Visit 6). These results won’t be acquired directly from the MMRM model. Rather, they will be obtained from the same model by forming appropriate estimate statements with the same algorithm across dulaglutide 3.0 mg and dulaglutide 4.5 mg.

- 3) Geometric LS means and corresponding 95% CIs of pancreatic enzyme for dulaglutide 3.0, dulaglutide 4.5 after adjusting for baseline, and the ratio between each combined treatment across algorithms and placebo, and the difference between each combined treatment to Dulaglutide1.5 at the same Week (Visit): Week 6 (Visit 6), Week 18 (Visit 12). These results will be obtained through the same model by forming appropriate estimate statements for the same dose across different algorithms.
- 4) The ratio of geometric LS means and the corresponding 95% CIs along with the p-value between each maintenance visit (Week 18/Visit 12) and the end of titration (Week 6/Visit 6) within the same treatment including the dulaglutide 3.0 mg, and 4.5 mg, and within the same algorithm will be presented. Any result related to combined treatment across algorithms and each algorithm at Visit 6 (Week 6) will be formed by constructing an appropriate estimate statement.

